6.4. General Methods

6.4.1. Data Handling After End of Double-blind Period

Data after the EODB period may not undergo the cleaning process and will not be displayed in any listings or used for summary statistics, statistical analyses, or imputations for the primary CSR.

6.4.2. Standard Derivations and Reporting Conventions

The following conversion factors will be used to convert days into weeks, months or years: 1 week=7 days, 1 month=30.4375 days, and 1 year=365.25 days.

The following derivations will be implemented.

• Age (years)=(date of informed consent-date of birth+1)/365.25

If only day of birth is missing: Age (years): (year/month of informed consent-year/month of birth)

If day and month of birth are missing: Age (years): (year of informed consent-year of birth)

The integer part of the calculated age will be used for reporting purposes.

- Body mass index (BMI, kg/m²)=weight (kg)/height (m)²
- Duration (in days) from a reference date (eg, randomization date, start date of study treatment)=

date of event-reference date + 1, if the date of the event is on or after the reference date

date of event-reference date, if the date of the event is before the reference date

Reporting conventions will be as follows:

• Mean (including arithmetic mean and geometric mean) and median will be displayed to one more decimal place than the raw data.

- Standard deviation (SD) will be displayed to two more decimal places than the raw data.
- Percentages (including percent changes from baseline for whole blood concentration of 2,3-DPG and ATP, relative standard deviation [RSD %], arithmetic coefficient of variation [CV%], and geometric coefficient of variation [CV% geometric mean]) will be displayed to 1 decimal place (however, percentages corresponding to 0 counts will be reported as 0 rather than 0.0 and 100 percent will be reported as 100 rather than 100.0).
- p-values will be reported with 4 decimal places; all p-values should be specified to be 1-sided or 2-sided.
- Unless otherwise specified, rounding will be performed to the closest integer/first decimal using the common mid-point between the two consecutive values, eg, 5.11 to 5.14 will be rounded to 5.1, and 5.15 to 5.19 will be rounded to 5.2.
 - Non-zero percentages that are <0.1 before rounding will be displayed as "<0.1", eg, 0.09 will be reported as <0.1 rather than as 0.1.
 - p-values<0.0001 before rounding will be displayed as "<0.0001", eg, a
 p-value of 0.00009 will be displayed as <0.0001 rather than as 0.0001.
- PK parameters will be reported to 3 significant figures, except for T_{max} and T_{last} which will be reported to 2 significant digits.

Note that some PK parameters are observed values (eg, C_{max}), while other PK parameters are derived from the intensive PK profiles (eg, AUC_{0-last}). For all the PK parameters, regardless of whether they are observed or derived, the individual PK parameter values are considered "raw data" when implementing the above reporting rules.

6.4.3. Pooling of Data Across Sites

In order to provide overall estimates of treatment effects, data will be pooled across sites. The "site" factor will not be considered in statistical models or subgroup analyses given the high number of participating sites in contrast to the anticipated small number of subjects randomized at each site.

6.4.4. Continuous and Categorical Variables

Continuous variables will be summarized using descriptive statistics, ie, number of nonmissing values, mean, SD, median, quartiles, minimum, and maximum. PK concentrations and parameters will be further summarized using arithmetic mean together with the CV% and 90% CI, geometric mean together with CV% geometric mean and 90% CI. PD concentration and parameters will be further summarized using arithmetic mean together with the CV% and 95% CI, geometric mean together with the CV% and 95% CI, and RSD% (applicable to PD concentration only).

Categorical variables will be summarized by frequency distributions (number and percentage of subjects within a given category in the analysis data set). Unless otherwise specified, the calculation of percentages will include the "missing" category. Therefore, counts of missing observations will be included in the denominator and presented as a

separate category. For summaries by visit, percentages will be based on the number of subjects with data available for that visit, unless otherwise specified.

6.4.5. Unscheduled Visits

Generally, data collected at unscheduled visits will be included and summarized for both safety and efficacy analyses in the same manner as the data collected at scheduled visits. PK and PD data collected at unscheduled visits will be listed and may not be summarized. Descriptive statistics (mean, SD, median, quartiles, minimum, and maximum) by nominal visit or time point for safety endpoints such as clinical laboratory measurements and vital signs will include only data from scheduled visits.

Summaries of outliers [eg, worst value, worst change from baseline, worst Common Terminology Criteria for Adverse Events (CTCAE) grade] during the on-treatment period for safety endpoints such as AEs, vital signs, and clinical laboratory measurements will include data from both scheduled and unscheduled visits.

For the evaluation of transfusion burden, iron metabolism (Section 7.6.3.2),

and bone

mineral density (BMD) by dual-energy x-ray absorptiometry scan (DXA, Section 7.7.5), data collected at unscheduled and scheduled postbaseline visits will be mapped to scheduled visits using analysis visit windows, and then values at scheduled postbaseline visits will be derived based on the rules described below. Descriptive statistics by nominal visit and longitudinal plots will be provided using the derived values at scheduled visits.

Analysis Visit Windows

For the evaluation of iron metabolism (Section 7.6.3.2),

and BMD by DXA scan (Section

7.7.5), the analysis visit windows will be derived based on the target study day for the scheduled visits as follows. Note that based on the schedule of assessments, a Week 4 Visit, for example, will have a target study day of $1+(4\times7)=29$.

For the Double-blind Period:

- Visit windows will be implemented for scheduled visits after study day 1 (ie, starting at Week 4 through the end of the Double-blind Period on Week 48).
- For analysis visit(n):
 - Start day of visit window =1+end day of window for visit(n-1). If n=1, start day of the visit window is study day 2
 - End day of visit window = [(target day for analysis visit(n) + target day for analysis visit(n+1))/2]-1 for Week < 48. The end day of visit window for Week 48 is the end of the Double-blind Period
 - Consistent with the rules above, for DXA scan results and which are only scheduled at Week 48, the analysis

visit window for Week 48 will start on study day 2. The end day of visit window for Week 48 is the end of the Double-blind Period

For the OLE Period:

- Visit windows will be implemented for all scheduled visits after the first dose of mitapivat in the OLE Period. Week 312 is the last scheduled visit in the OLE Period.
- For analysis visit(n):
 - Start day of visit window = 1+ end day of window for visit(n-1). If n=1, start day of the visit is the day after the first dose of mitapivat in the OLE Period.
 - End day of visit window = [(target day for analysis visit(n) + target day for analysis visit(n+1))/2]-1 for Week < 312. The end day of visit window for Week 312 is the EOS date.

Derivation of Values at Scheduled Postbaseline Visits Based on Analysis Visit Windows

For laboratory parameters [transfusion burden, iron metabolism (Section 7.6.3.2),

, if multiple assessments are identified

within a visit window for a parameter, then

- Central laboratory assessment(s) (scheduled or unscheduled) within the visit window will be used
- If no central laboratory value is within the visit window, local laboratory assessment(s) within the visit window will be used

For the evaluation of transfusion burden, iron metabolism (Section 7.6.3.2),

, and BMD by

DXA scan (Section 7.7.5), if multiple assessments are identified within a visit window for a parameter and after selecting the assessments for laboratory parameters as described above, the following rules will be applied:

- The assessment measured closest to the target study day of the scheduled visit will be used
- If there are multiple assessments equidistant to the target study day
 - the average value will be used for laboratory parameters
 - the later assessment will be used for and BMD by DXA scan

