²⁴Blood samples for pharmacokinetic and pharmacodynamic analysis will be collected at Week 12 (≤60 min predose) and Week 24 (≤60 min predose). If an RBC transfusion takes place during this visit, the blood samples for pharmacokinetic and pharmacodynamic analysis should be collected before the RBC transfusion.

²⁵Blood samples for pharmacokinetic and pharmacodynamic analysis will be collected at Week 36 (≤60 min predose, and 0.5 hr [±5 min], 1 hr [±5 min], 3 hr [±15 min], 5 hr [±15 min], and 7 hr [±30 min] postdose). If an RBC transfusion takes place during this visit, the blood samples for pharmacokinetic and pharmacodynamic analysis should be collected before the RBC transfusion.

²⁸ Study drug will be dispensed at every visit. Subjects must return study drug bottles (including empty bottles) and unused tablets at each visit to the clinical study center. The morning dose of study drug will be administered at the clinical study center during in-person visits to the clinical study center. During the Double-blind Period, subjects will be asked to record study drug dosing in a diary. The last dose of blinded study drug will be administered on the morning of the Week 48 visit. The first dose of open-label mitapivat will be administered on the evening of the Week 48 visit.

²⁹ Adverse events and SAEs will be collected throughout the study.

³⁰Concomitant medications, procedures, and surgeries are defined as all medications administered and procedures conducted from the first dose of study drug through 4 weeks after administration of the last dose of study drug (ie, EOS visit).

³¹ During the study, the subject's RBC transfusion schedule will be modified according to the guidance in Section 8.7. Information to be recorded for each transfusion is also in this section.

							O	pen-lab	el Exte	ension 1	Period	l						Safety Follow- up ²
Study Visit Week:	120	132	144	156 ³	168	180 ³	192	204 ³	216	228 ³	240	252 ³	264	276 ³	288	300 ³	312 ⁴	28 Days
Study Visit Day:	841	925	1,009	1,093	1,177	1,261	1,345	1,429	1,513	1,597	1,681	1,765	1,849	1,933	2,017	2,101	2,185	After Last Dose/ EOS
Study Visit Window (Days):	±14	±14	±14	±14	±14	±14	±14	±14	±14	±14	±14	±14	±14	±14	±14	±14	±14	+4
Procedures:																		
Pregnancy testing (WOCBP only) ⁵																		Х
BMD by DXA scan ⁶			Х				Х				Х				Х			
Physical examination																	Х	Х
Vital signs and weight ⁸	Х	Х	Х		X		Х		Х		Х		Х		Х		Х	Х
Hematology ⁹	Х	Х	Х		X		Х		Х		Х		Х		Х		Х	Х

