2. INTRODUCTION

This SAP provides the detailed methodology for summary and statistical analyses of the data collected in Study AG348-C-018. This document may modify the plans outlined in the protocol; however, any major modifications of the primary endpoint definition or its analysis will also be reflected in a protocol amendment.

The primary clinical study report (CSR) will include all data for each subject up to the end of Double-blind (EODB) Period. The EODB period is defined as the end of the safety follow-up (for subjects who discontinue study treatment during the Double-blind Period) or before the start of study treatment in the Open-label Extension (OLE) Period (for subjects who continue onto the OLE Period after completing the Double-blind Period).

A CSR addendum will include data (associated with objectives that encompass OLE Period evaluations) through the End of Study (EOS). The EOS is defined as the time at which all subjects complete all study visits, are lost to follow-up, have withdrawn consent for further participation in the study, or when the Sponsor terminates the study. Study completion is the date of the last visit of the last subject in the study.

[figure not shown]
In the following sections, references to "EODB period date/EOS date" are meant to indicate that the EODB period subject-specific dates will be used for analyses to be reported in the primary CSR and the EOS date will be used for analyses to be reported in the addendum CSR.

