6.3.5. On-Treatment Period

The on-treatment period starts on the date of the start of study treatment and ends 28 days after the end of study treatment (including dose taper period).

Within the on-treatment period, there are two distinct treatment periods:

- Double-blind on-treatment period starts on the date of the start of study treatment and ends
 - 28 days after the end of study treatment, for subjects who discontinue study treatment during the Double-blind Period of the study
 - Before the start of the OLE treatment period, for subjects who continue onto the OLE Period of the study

• OLE on-treatment period applies only to subjects who complete the Doubleblind Period of the study, and starts with the first dose of open-label mitapivat in the OLE Period and ends 28 days after the end of study treatment.

For subjects who receive mitapivat in the OLE Period, assessments or events occurring on the date of first dose of mitapivat in the OLE Period will be included in the analysis of the data from the double-blind on-treatment period, except for AEs and concomitant medications reported for subjects in the placebo arm which will be included only in the analysis of the data from the OLE on-treatment period.

Data listings will include all assessments and events, with those that occur outside of the on-treatment period flagged.

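### For subjects entering the open-label extension, a Week 48 DXA scan made on a date after the Week 48 visit but by Day 349 is left out of the double-blind bone density summaries and assigned to Week 96

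*SAP*

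**What the plan says.** **Week 48 DXA window (SAP 6.4.5).** DXA has one post-baseline time point in the Double-blind Period, so its "visit window for Week 48 will start on study day 2". It closes as follows: "The end day of visit window for Week 48 is the end of the Double-blind Period".

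**End of the Double-blind Period (SAP 2).** For subjects who stop treatment early it is "the end of the safety follow-up (for subjects who discontinue study treatment during the Double-blind Period"). For those who continue it is "before the start of study treatment in the Open-label Extension (OLE) Period (for subjects who continue onto the OLE Period").

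**First open-label dose (Protocol 1.2, study drug footnote to Table 1).** "The first dose of open-label mitapivat will be administered on the evening of the Week 48 visit".

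**Same-date rule (SAP 6.3.5).** For OLE participants, "assessments or events occurring on the date of first dose of mitapivat in the OLE Period will be included in the analysis" of the double-blind on-treatment data. The exceptions concern adverse events and concomitant medications in the placebo arm, not scans.

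**Later data (SAP 6.4.1).** Data after the end of the Double-blind Period "will not be displayed in any listings or used for summary statistics, statistical analyses, or imputations for the primary CSR".

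**First OLE window (SAP 6.4.5).** The "start day of the visit is the day after the first dose of mitapivat in the OLE Period".

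**Schedule (Protocol 1.2).** Week 48 is Day 337 with a visit window of ±12 days. DXA is listed at screening, Week 48 and Week 96, then at Week 144 and later visits. Its footnote names only the sites scanned.

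**The concern.** Protocol 8.6.4 makes bone density a monitor for potential aromatase inhibition. Week 48 is the only post-baseline scan with a concurrent placebo arm, because everyone in the OLE receives mitapivat. The analysis window closes on the day of the Week 48 visit, whereas the protocol's calendar for Week 48 runs to Day 349. Nothing in the protocol text ties the scan to the visit day or places it before the first open-label dose. Blood samples, by contrast, must precede dosing and any same-day transfusion.

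A scan made for Week 48 on a later date would be missing from the primary study report's BMD and T-score summaries. In the OLE data it would carry the wrong visit label or be passed over. In placebo subjects it could also distort change from baseline on open-label drug.

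**Working it through.** **1. Reproduce the plan's days.** The SAP 6.4.5 rule is target day = 1 + 7 × week.

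- Week 4: 1 + 28 = 29, the SAP's own example.
- Week 48: 1 + 336 = 337, as in Protocol Table 1.
- Week 96: 1 + 672 = 673, as in Protocol Table 1.
- Week 144: 1 + 1008 = 1009, as in Protocol Table 2.

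The protocol window for Week 48 is 337 − 12 = Day 325 to 337 + 12 = Day 349, which is 25 days.

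**2. Close the Week 48 DXA window for an OLE entrant.** The first open-label dose falls on the visit date, and the same-date rule keeps scans made that day. The last usable day is therefore the visit day V. The days that are inside the protocol window but outside the analysis window number 349 − V.

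| Visit and first OLE dose | Protocol-window days after closure | Share of 25 days |
|---|---|---|
| Day 325 | 24 | 96% |
| Day 331 | 18 | 72% |
| Day 337 | 12 | 48% |
| Day 343 | 6 | 24% |
| Day 349 | 0 | 0% |

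These are calendar days, not shares of subjects. As an example, a subject seen on Day 330 and scanned on the exact target day, 337, has no Week 48 value.

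**3. Follow the late scan.** The next scheduled DXA is Week 96. Its analysis window opens the day after the first open-label dose and ends at (673 + 1009)/2 − 1 = Day 840. With the visit on Day 337, a late scan on Days 338 to 349 lies 673 − 338 = 335 to 673 − 349 = 324 days before the Week 96 target. SAP 6.4.5 takes the scan closest to target. If a Week 96 scan exists near its target, the late scan is passed over in the by-visit table. If none exists, the late scan is reported as Week 96.

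**4. Placebo subjects' OLE baseline.** SAP 6.3.4.2 takes the last assessment before open-label mitapivat. A late scan does not qualify, so without another double-blind scan the baseline falls back to screening (Day −56 to Day −1). With the first open-label dose on Day 337 and no Day 0, that is 336 + 1 = 337 to 336 + 56 = 392 days earlier. Change during the placebo year would then be counted in the change on open-label mitapivat. The late scan would also enter the OLE worst-T-score shift table (SAP 7.7 and 7.7.5).

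**5. Number of scans.** The documents give no share of late scans and no number of OLE entrants. Taking all 240 randomized subjects (160 and 80) as the base gives:

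| Assumed share late | Mitapivat | Placebo | Total |
|---|---|---|---|
| 2% | 3.2 | 1.6 | 4.8 |
| 5% | 8 | 4 | 12 |
| 10% | 16 | 8 | 24 |
| 20% | 32 | 16 | 48 |

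Only OLE entrants can be affected, so the counts are somewhat lower for any given share.

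**The case against.** The strongest reply is that a separate-day scan is assumed. The ±12 days is labelled a window for the visit, and Protocol 4.2 says the windows exist to align visits with transfusion schedules. Week 48 is not among the visits with a home option. The first open-label dose moves with the visit, so a late visit with a same-day scan loses nothing. This stands in part: that a later scan complies with the protocol is inferred from silence, and the frequency is unknown and may be very small. It does not remove the gap, because the SAP would mishandle such a scan if it occurred.

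Much is already covered. Scans before the visit count back to study day 2, same-date scans count, and subjects who discontinue keep the window open through safety follow-up. All of this stands and limits the point to OLE entrants scanned on a later date.

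Closing at first open-label exposure is also a clean rule that keeps mitapivat-exposed scans out of the placebo summary. That is a fair reason for it, and the documents contain no evidence on how fast bone density could respond. It is why late scans should be flagged, not merged without comment.

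A reader might infer that a confidence interval for the arm difference would widen. The documents do not support this: Protocol 10.4.4.3 and SAP 7.7.5 plan only summaries and shift tables for DXA, with no between-arm interval or test. A reader might also infer that late scans are deleted. They are not; they belong to the OLE data for the report addendum.

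**Conclusion.** The point holds as a narrow gap in the visit-window rules. For an OLE entrant, a Week 48 scan made after the date of the first open-label dose and by Day 349 is lost from the only placebo-controlled bone density summaries. It is either passed over or labelled Week 96, and it cannot be a placebo subject's OLE baseline. The chain of rules is explicit. What is assumed is that scans are sometimes made on a separate later date, and how often: about 5 to 48 scans at shares of 2% to 20% of 240. The consequence is missing or misattributed values in descriptive safety tables. The primary endpoint and type I error are unaffected. It is worth correcting because the correction is cheap and a lost controlled value cannot be replaced later.

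**What to change.** Amend the SAP before database lock, for DXA only and for subjects who enter the OLE:

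- **6.4.5:** end the Week 48 window at the later of the end of the Double-blind Period and Day 349, and start the Week 96 window the next day. The limit should be the fixed Day 349. First open-label dose plus 12 days is not the protocol limit: a visit on Day 345 would give Day 357, and a visit on Day 325 only Day 337.
- **6.4.1, 6.3.5 and 7.7:** exempt these scans from the data cut-off and from the on-treatment period limits, so that they are cleaned and summarized as double-blind data.
- **6.3.4.2:** allow such a scan as the OLE baseline for placebo subjects.
- **7.7.5:** flag scans made after the first open-label dose, and provide a listing or a summary without them.

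The cost is a few sentences and the cleaning of the affected DXA records. The downside is that some placebo scans would follow open-label mitapivat, by at most 349 − 325 = 24 days, or 12 days if the visit is on target. The listing or the summary without flagged scans would show any effect of that.

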7.6.1. Primary Endpoint

The primary endpoint is the transfusion reduction response (TRR), defined as a \geq 50% reduction in transfused RBC units with a reduction of \geq 2 units of transfused RBCs in any consecutive 12-week period through Week 48 compared with the baseline transfusion burden (defined in Section 6.3.4.1) standardized to 12 weeks.

- Baseline transfusion burden standardized to 12 weeks (units/12-weeks) = total number of RBC units transfused during the 24-week period before the 'reference date'×12/24
- Reduction from baseline in transfusion burden for a 12-week period = Baseline transfusion burden standardized to 12 weeks Number of transfused RBC units in the 12-week period
- Percent reduction from baseline in transfusion burden for a 12-week period =100×(Baseline transfusion burden standardized to 12 weeks Number of transfused RBC units in the 12-week period)/ Baseline transfusion burden standardized to 12 weeks

Subjects who are withdrawn from the study before Week 12 (Day 85) will be considered nonresponders. A subject will meet the primary endpoint if, in any 12-week (84 days) consecutive period from the date of first dose in the Double-blind Period (Day 1) through Week 48 in the Double-blind Period both conditions below are met:

- Reduction from baseline in transfusion burden ≥ 2 RBC units
- Percent reduction from baseline in transfusion burden is $\geq 50\%$

The consecutive 12-week periods for the evaluation are Day 1 through Day 84, Day 2 through Day 85, and so on to cover all 84-day periods through Week 48 in the Double-blind Period.

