7.6.2. Key Secondary Endpoints

The key secondary endpoints are

• TRR2, defined as ≥50% reduction in transfused RBC units in any consecutive 24-week period through Week 48 compared with the 24-week baseline transfusion burden (defined in Section 6.3.4.1). The consecutive 24-week

periods for the evaluation are Day 1 through Day 168, Day 2 through Day 169, and so on to cover all 168-day periods through Week 48 in the Double-blind Period.

- TRR3, defined as ≥33% reduction in transfused RBC units from Week 13 through Week 48 compared with the baseline transfusion burden standardized to 36 weeks.
- TRR4, defined as ≥50% reduction in transfused RBC units from Week 13 through Week 48 compared with the baseline transfusion burden standardized to 36 weeks.

Baseline transfusion burden standardized to 36 weeks (units/36-weeks) = 24-week baseline transfusion burden (defined in Section 6.3.4.1)×36/24

Transfusion burden from Week 13 through Week 48 standardized to 36 weeks (units/36 weeks) = Number of transfused RBC units from Day 85 through Week 48 in the Double-blind Period \times 36/(Number of days from Day 85 through Week 48 in the Double-blind Period/7)

Percent reduction from baseline =100×(Baseline transfusion burden standardized to 36 weeks – Transfusion burden from Week 13 through Week 48 standardized to 36 weeks)/ Baseline transfusion burden standardized to 36 weeks

These endpoints (TRR2, TRR3, and TRR4) will be tested using the Mantel-Haenszel stratum weighted method adjusting for randomization stratification factors. The response rate based on the different definitions of response will be summarized for each treatment arm. The adjusted differences in response rate between the mitapivat arm and placebo arm, along with the 95% CI and the 2-sided p-value, will be provided.

Subjects who are withdrawn from the study before Week 24 (Day 169) will be considered nonresponders in TRR2. Subjects who are withdrawn from the study before Week 48 will be considered nonresponders in TRR3 and TRR4.

The following sensitivity analyses will be performed for each of these endpoints:

- TRR2, TRR3, TRR4 will be analyzed using the methodology described for the primary analysis but based on PPS.

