7.6.3.2. Iron Metabolism

Iron metabolism will be assessed based on iron, serum ferritin, total iron binding capacity, and transferrin saturation.

Values and changes from baseline will be summarized based on descriptive statistics, by treatment arm and study visit, through Week 48 of the Double-blind Period. Change from baseline will be compared between treatment arms following the same methodology as described in Section 7.6.3.1 for reduction from baseline in RBC transfusion burden.

By-subject longitudinal plots will be presented with values at baseline and postbaseline, transfusions, and prescribed dose over time. The plots will further include TRR status, treatment arm, age, sex, race, randomization stratification factors, 24-week baseline transfusion burden, and hydroxyurea status.

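### SAP 6.4.5 wrongly puts transfusion burden under a one-record-per-visit-window laboratory rule; the endpoint formulas are not affected, so this is a clean-up

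*SAP*

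**What the plan says.** SAP 6.4.5 (Unscheduled Visits) names transfusion burden three times.

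1. The list of data mapped to scheduled visits through analysis windows opens "For the evaluation of transfusion burden, iron metabolism (Section 7.6.3.2". The stated use of the result is: "Descriptive statistics by nominal visit and longitudinal plots will be provided using the derived values at scheduled visits".
2. The list under central-over-local selection opens "For laboratory parameters [transfusion burden, iron metabolism (Section 7.6.3.2", so transfusion burden is classed as a laboratory parameter.
3. The list under the rule for several records in one window names it again. The rule is: "The assessment measured closest to the target study day of the scheduled visit will be used". If records are equally far from the target day, laboratory parameters are averaged.

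The paragraph that builds the windows opens "For the evaluation of iron metabolism (Section 7.6.3.2" and, as far as it is legible, does not name transfusion burden.

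Elsewhere the SAP counts units:

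- Section 6.3.4.1 takes baseline as all units over 168 days.
- Section 7.6.1 uses "Number of transfused RBC units in the 12-week period", for 84-day periods that move forward one day at a time.
- Section 7.6.2 does the same over 168-day periods for TRR2. For TRR3 and TRR4 it uses "Number of transfused RBC units from Day 85 through Week 48 in the Double-blind Period".
- Section 7.6.3.1 repeats that last count for the Week 13 to 48 change.

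Protocol 1.2 records on-treatment transfusions continuously. Protocol 8.7 requires every transfusion to be recorded, with its date and number of units.

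**The concern.** Keeping the record nearest a target day suits a repeated measurement such as ferritin, where each record estimates the same quantity. A transfusion record is an addend: the burden over an interval is the sum of the units given in it. Taking the nearest record discards units, and averaging tied records does too. Two 2-unit transfusions equally far from the target day average to 2 units, while the burden is 2 + 2 = 4. Central-over-local selection has no meaning here, because a transfusion has no central laboratory value. A continuously recorded event has no target study day either.

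Two things are at stake. First, the SAP holds two incompatible derivations for a variable that underlies the primary and all key secondary endpoints. Second, a by-visit transfusion display made under 6.4.5 would leave out transfusions whenever more than one falls in a window. The loss would be greatest in the most frequently transfused subjects, and the display could disagree with the endpoint counts in the same report.

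**Working it through.** **Can both rules govern the same variable?** The plan gives no figure for this point, so the first check sets the texts side by side. If Week 48 closes at Day 336, section 7.6.1 needs a unit count for 336 − 84 + 1 = 253 overlapping 84-day periods. Section 6.4.5 gives at most one value per visit window, which is 12 values on a 4-weekly visit schedule. Twelve values cannot supply 253 day-by-day sums. The 6.4.5 rule therefore cannot be the route to TRR, and the same reasoning applies to the rolling 168-day periods of TRR2. For TRR3, TRR4 and the Week 13 to 48 change, 7.6.2 and 7.6.3.1 write out the count explicitly.

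**What would a display lose?** This part is an illustration, because the documents give neither transfusion windows nor a distribution of transfusion intervals.

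Inputs:
- Target days: 1 + 7 × week, the SAP 6.4.5 convention. Week 4 gives 1 + 28 = 29, which is the SAP's own example.
- Visits: Weeks 4, 8, …, 48, the Double-blind visits in Protocol 1.2 (an assumption for transfusions).
- Window end, from 6.4.5: (target of this visit + target of next visit)/2 − 1.
- Exact transfusion schedules (assumed). Transfusion 0 is placed 1 to 7 days before Day 1, within the limit in Protocol 8.7.

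Windows:
- Week 4: (29 + 57)/2 − 1 = 42, so Day 2–42
- Week 8: (57 + 85)/2 − 1 = 70, so Day 43–70
- then 28-day windows up to Week 44: (309 + 337)/2 − 1 = 322, so Day 295–322
- Week 48: Day 323 to the end, taken as Day 336

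Worked case, every 21 days, with Transfusion 0 one day before Day 1. Transfusions fall on Days 21, 42, 63, …, 336, which is 336/21 = 16. Four windows hold two each: Days 21 and 42; 105 and 126; 189 and 210; 273 and 294. The other eight windows hold one each. Kept: 12. Dropped: 4/16 = 25%. All seven starting positions give the same result.

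| Interval (days) | Given, Day 2–336 | Kept | Dropped |
|---|---|---|---|
| 17 | 19–20 | 11–12 | 37–42% |
| 21 | 16 | 12 | 25% |
| 24 | 14 | 12 | 14% |
| 28 | 12 | 12 | 0% |
| 35 | 9 | 9 | 0% |
| 42 | 8 | 8 | 0% |

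Under these assumptions, a subject with 16 transfusions and one with 12 would both be displayed with 12. Closing the period at Day 337 does not change the table.

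**The case against.** The strongest reply is that nothing legible goes wrong. Section 6.4.5 ties its derived values to by-visit statistics and longitudinal plots, and section 7.6.3.1 plans no by-visit transfusion summary. It plans interval counts, percentage categories, an ANCOVA and transfusion independence. The one nearby output is in 7.6.3.2: "By-subject longitudinal plots will be presented with values at baseline and postbaseline, transfusions, and prescribed dose over time". There the windowed values are the iron parameters. Transfusions stand beside prescribed dose and read most naturally as events plotted on their dates. Text next to the 6.4.5 lists is also removed from the public copy, so a by-visit transfusion display, or windows for one, may be defined where it cannot be seen. All of this stands, and it is why the point is low in severity. It does not rescue the rule: the term is legible in all three lists, and a nearest-record or averaging rule is wrong for a unit count in any display.

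A reader might infer more than the documents support, in two ways.

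- **That TRR to TRR4 would be computed from window-reduced records, giving false responders and lost power.** The specific formulas in 7.6.1, 7.6.2 and 7.6.3.1 govern those analyses, and one value per window could not supply the rolling sums.
- **That the sparse iron-panel windows (Weeks 24 and 48) apply to transfusions, so that most records would be lost.** No text links those windows to transfusion data.

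**Conclusion.** SAP 6.4.5 states a rule that gives a wrong value for transfusion burden and is inconsistent with how the rest of the SAP counts units. This is more than missing detail, because 6.4.5 says its derived values will be used for by-visit statistics and longitudinal plots. The consequence is limited to any by-visit transfusion-burden statistics or plots made under 6.4.5. No change to TRR, TRR2 to TRR4, the Week 13 to 48 change, alpha, power or sample size is claimed.

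The 25% loss at 21-day intervals rests on assumed 4-weekly windows and perfectly regular schedules. Under the same assumptions nothing is lost at 28, 35 or 42 days. No trial-level figure follows from the documents. Severity is low: clean-up of a wrong rule.

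**What to change.** Delete transfusion burden from the three lists in SAP 6.4.5. Add one sentence along these lines: RBC units are summed over all recorded transfusions by date within the interval being summarised; analysis visit windows, closest-record selection and central/local selection do not apply to transfusion data, including any by-visit display.

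The cost is SAP wording only. No endpoint definition, sample size, alpha, stated power or data collection changes.
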